STATISTICAL ANALYSIS PLAN

Study title: A multi-centre randomised controlled trial to compare the effectiveness of admission avoidance hospital at home with comprehensive geriatric assessment vs. inpatient comprehensive geriatric assessment on the number of frail older people 'living at home'

Short title: Randomised controlled trial (RCT) of comprehensive geriatric assessment (CGA) in a hospital at home (HAH) setting

Ethics ref: 14/WA/1081 (England, Wales & Northern Ireland); 14/SS/1046 (Scotland)

Version number and date: Version 1.0 15 March 2019

	NAME	TITLE	SIGNATURE	DATE
Written by:	[name]	Trial Statistician		
Reviewed by:	[name]	Senior Trial Statistician		
Approved by:	[name]	Chief Investigator		

Version History

Version:	Version Date:	Changes:
1.0	15 March 2019	Original version

TABLE OF CONTENTS

TABLE OF CONTENTS.....	2
1 INTRODUCTION.....	3
1.1 PREFACE	3
1.2 PURPOSE AND SCOPE OF THE PLAN	3
1.3 TRIAL OVERVIEW.....	4
1.4 OBJECTIVES	4
2 TRIAL DESIGN	4
2.1 OUTCOMES MEASURES	4
2.1.1 Primary outcome for the primary objective	4
2.1.2 Secondary outcomes for the primary objective	5
2.2 TARGET POPULATION.....	7
2.3 SAMPLE SIZE	8
2.4 RANDOMISATION AND BLINDING IN THE ANALYSIS STAGE	8
3 ANALYSIS – GENERAL CONSIDERATIONS	9
3.1 DESCRIPTIVE STATISTICS	9
3.2 CHARACTERISTICS OF PARTICIPANTS.....	9
3.3 DEFINITION OF POPULATION FOR ANALYSIS	9
3.4 POOLING OF INVESTIGATIONAL SITES.....	9
3.5 DATA MONITORING COMMITTEE AND INTERIM ANALYSES	9
4 PRIMARY ANALYSIS.....	9
4.1 PRIMARY OUTCOME	9
4.2 HANDLING MISSING DATA.....	10
4.3 HANDLING OUTLIERS	10
4.4 MULTIPLE COMPARISONS AND MULTIPLICITY	10
4.5 MODEL ASSUMPTIONS.....	10
5 SECONDARY ANALYSIS	10
5.1 SECONDARY OUTCOMES.....	10
5.2 TERTIARY/OTHER OUTCOMES.....	12
6 SENSITIVITY ANALYSIS.....	12
7 SUBGROUP ANALYSES.....	13
8 ADDITIONAL EXPLORATORY ANALYSIS.....	13
9 SAFETY ANALYSIS	13
9.1 ADVERSE EVENTS	14
10 VALIDATION	14
11 CHANGES TO THE PROTOCOL OR PREVIOUS VERSIONS OF SAP	14
12 REFERENCES	15
13 APPENDICES	16

The details regarding analysis of the cost-effectiveness, process evaluation and qualitative study will be detailed in a separate analysis plan.

The CGA trial will be analysed after the 6 months follow-up data has been collected and before 12 months follow-up. The analysis of 12 month follow-up data will be reported in a separate statistical analysis report to the main trial findings (i.e. 6 month outcome).

1.3 TRIAL OVERVIEW

Hospital admissions among older adults with frailty are increasing. The evidence supporting the adoption of acute care is from small trials, and it is uncertain if acute care in the home with CGA improves health outcomes or reduces cost compared with inpatient admission with CGA.

1.4 OBJECTIVES

The primary objective in the protocol outlines both the effectiveness and cost-effectiveness of admission avoidance. The secondary objective focuses on a process evaluation. All objectives related to health economics will not be mentioned or detailed in this analysis plan.

Primary Objective

1. To test the effectiveness and cost-effectiveness of admission avoidance hospital at home (HAH) with CGA compared with hospital admission with CGA and investigate the generalizability and cost-effectiveness of CGA in settings where health and social care provision vary.

Secondary objectives

All objectives unrelated to the main statistical analysis and will be outlined elsewhere.

2 TRIAL DESIGN

The study is a multi-site open randomised controlled trial. Participants will be randomised using a 2:1 ratio to either the intervention arm of admission avoidance HAH with CGA or the control arm of hospital inpatient CGA. The patient population is older people with frailty and a level of disability, who are the target population for HAH services.

Sites are Bradford, Newport & Torfaen, Lanarkshire, Lothian, Fife, Royal Devon Exeter, North Devon, Southern Trust, Guys & St. Thomas, and Belfast.

See Appendix I for a time schedule of trial procedures.

2.1 OUTCOMES MEASURES

Outcomes are measured at baseline, 6 months and 12 months (excluding delirium which is measured at 3 days, 5 days and 1 month) after randomisation. Data will be entered directly onto CRFs and e-CRFs

See Appendix II for a table of outcome assessment schedule.

2.1.1 PRIMARY OUTCOME FOR THE PRIMARY OBJECTIVE

The primary outcome is 'living at home' at 6 months.

Living at home is defined as the inverse of death or living in a residential care setting. It is derived from a place of assessment variable, (a 5-category variable, 1 = hospital assessment centre, 2 = in-patient hospital, 3 =

residential care home, 4 = patient's home, and 5 = other) and the patient's death status (0 = alive, 1 = dead) reported at the 6 months visit. Living at home will be coded as a binary variable (1 = alive and living at home, 0 = otherwise (including deaths and living at residential care). Living at home will be computed as 0 if death status = 1 (dead) or place of assessment = 3 (residential care home), or place of assessment = 5 (other) and other = "Nursing Home" (variable *assessoth6m*), otherwise living at home = 1, as long as patient also has a visit date for the particular time point.

Additional information about the residential care (variable *admitryr*) will be used for patients with a place of assessment = 1 (hospital assessment centre) or = 2 (in-patient hospital) to verify where these patients were admitted from. If patients have been in residential care they will be coded as 'not living at home', if patients are not recorded as having been in residential care then they will be assumed to have been admitted from 'home'.

If the patient's death status is missing and the patient's place of assessment has been completed, the patient will be assumed to be alive. In cases where the place of assessment and death status are conflicting (i.e. place of assessment is complete but the patient has been reported as dead) then the patient death form CRF will be used to confirm whether the patient is alive or dead. If the place of assessment and the patient's death status are both missing, then the primary outcome will be missing. This information will be coded as a binary variable (0 = death or not living at home, 1 = alive and living at home) to be used in the analysis.

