the patient death form CRF. If a patient has been reported as dead at 6 or 12 months on the follow-up CRF (variable *deathyn*) it will be checked against the date of death on the Patient Death CRF (variable *deathdat*). If there is conflicting information between the follow-up form and the death form, the death form will overrule the Follow up CRF. If neither the follow-up form nor the death form have been completed then the TM will check with the site if the patient has died.

3) New long-term residential care at 1 month and 6 months

Subsequent admission to residential care is measured at 1 month, and 6 months follow up (variable *admitryn*). This will be coded as a binary variable (0 = No, 1 = Yes). The 6 months admission to residential care data will include the data collected at the 1 month time point.

4) Cognitive impairment at baseline and 6 months (MoCA)

The Montreal Cognitive Assessment (MoCA) [2] is used to derive a variable for cognitive impairment, and is assessed at baseline and 6 months follow-up. The MoCA comprises 8 sections with a total of 30 questions administered by a qualified health professional (variables *mocavis mocanam mocaatt mocalan mocaabs mocarec mocaori*). A total MoCA score will be derived by summing the score from each section of the questionnaire, only patients with complete MoCA will have a total MoCA score computed, an extra point is added to the total score if the patient has 12 or less years of education. The possible range of scores for the MoCA range from 0 to 30, with a score of 26 or above is considered normal. If the patient is visually impaired or if they are frail and unable to write and draw, the visuospatial/executive section (variable *mocavis*) and the naming section (variable *mocanam*) are excluded and is scored out of 22 instead, a score of 18 or above is considered normal. Cognitive impairment will be coded as a binary variable (0 = score less than 26 (less than 18 if visually impaired), 1 = score 26 or more (18 or more if visually impaired)).

5) Activities of daily living at baseline and 6 months (Barthel index)

The Barthel index [3] is used to derive a variable for activities of daily living, and is assessed at baseline and 6 months follow-up. The Barthel index consists of 10 questions (variables *biadl1 – biadl10*), and has a possible range of scores from 0 (completely dependent) to 20 (completely independent). The final Barthel index score is derived by summing the 10 items.

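### Sections 2.1.1 and 2.1.2 settle death by 6 months by different rules, so a documented death can count as 'living at home' or as missing in the primary outcome

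*SAP*

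**What the plan says.** **Primary outcome (section 2.1.1).** 'Living at home' is derived from place of assessment and "death status (0 = alive, 1 = dead) reported at the 6 months visit". The value 1 is given to patients not coded 0, "as long as patient also has a visit date for the particular time point". Three further rules deal with gaps and clashes:

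- Death status blank, place present: "If the patient's death status is missing and the patient's place of assessment has been completed, the patient will be assumed to be alive".
- Place present, patient reported dead: "then the patient death form CRF will be used to confirm whether the patient is alive or dead".
- Both blank: "If the place of assessment and the patient's death status are both missing, then the primary outcome will be missing".

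Only the second rule uses the death form.

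**Mortality (section 2.1.2 item 2).** For a patient reported dead at 6 or 12 months on the follow-up CRF, "it will be checked against the date of death on the Patient Death CRF". Then: "If there is conflicting information between the follow-up form and the death form, the death form will overrule the Follow up CRF". If neither form has been completed, the trial manager asks the site.

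Section 2.1.1 does not refer to the mortality rule. Neither section defines 6 months as a fixed day after randomisation.

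**The concern.** Death is one of the two components of the primary composite and also a secondary outcome in its own right. Both should rest on the same determination of who had died by 6 months. Here the narrower rule governs the primary outcome, although the death form and the date of death are already collected.

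Two things are at stake. First, a known death may be analysed as a success, or left out of the primary model and then replaced or imputed under section 6 items 2 and 3, where one of the replacements is alive and at home. Second, the report could show a composite that disagrees with its own component for the same patient. The rule also carries forward: section 2.1.2 item 13 derives the 12-month outcome in the same way, and section 6 item 4 models both time points together.

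**Working it through.** The point concerns a derivation rule, so the main check is to follow individual patients through both sections.

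| Patient | Primary outcome (2.1.1) | 6-month mortality (2.1.2 item 2) |
|---|---|---|
| C. Visit date and place (own home) entered, death status blank, death form on file | 1, assumed alive; death form not consulted | Dead, from the death form |
| D. Place and death status both blank, death form on file | Missing; death form not consulted | Dead, from the death form |
| A. Seen alive at home before month 6, death form dates a death after the visit but before month 6 | 1 | Dead, if the overrule sentence covers a patient recorded alive |
| B. Dies after month 6 but before a late visit, recorded dead | 0 | Not a 6-month death only if a 6-month cut-off applies; none is stated |

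C and D do not depend on visit timing. For these two, mortality is read as dead because the site query applies only when neither form exists, so a filed death form must count. A needs a broad reading of the overrule sentence. B needs a cut-off that the SAP does not contain.

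**Denominators.** The SAP's own figure reproduces. Inputs from section 2.3: 50% v 40%, 2:1 allocation, N = 1050, 6% attrition; alpha 0.05 is taken as two-sided.

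- Evaluable patients: 1050 × 0.94 = 987, that is 329 control and 658 hospital at home.
- Pooled rate: (0.5 + 2 × 0.4)/3 = 0.4333. Null SE = √[0.4333 × 0.5667 × (1/329 + 1/658)] = 0.0335. Alternative SE = √[0.25/329 + 0.24/658] = 0.0335.
- Continuity correction: 0.5 × (1/329 + 1/658) = 0.0023.
- Power = Φ[(0.1 − 0.0023 − 1.96 × 0.0335)/0.0335] = 83.1% (unrounded SEs), against a stated figure of around 83%.

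**Effect of each miscoded death.**

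- Coded as a success (C): 1/329 = 0.30 points in control, 1/658 = 0.15 points in hospital at home.
- Coded as missing (D): dropping one event from an arm with event rate p lowers that rate by about (1 − p)/n. At the planning rates (stated for 12 months) this is 0.5/329 = 0.15 points and 0.6/658 = 0.09 points.

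The SAP gives nothing from which the number of C or D patients could be estimated.

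**Scale of case A, on assumptions not in the SAP.** Take 6-month mortality m of 10% to 25% and a constant weekly hazard h = −ln(1 − m)/26. The chance of dying in a gap of w weeks is q = 1 − exp(−h × w).

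- Two weeks early: q = 0.81% (m = 10%) to 2.19% (m = 25%). If a quarter of visits were that early: 987 × 0.90 × 0.0081/4 = 1.8 patients, to 987 × 0.75 × 0.0219/4 = 4.1.
- Four weeks early: q = 1.61% to 4.33%, giving 3.6 to 8.0 patients on the same basis.

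This is about 2 to 8 patients in the whole trial. It runs somewhat high, because not every survivor would be coded as living at home.

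**The case against.** The best defence is that the two sections need not disagree. The overrule sentence applies to conflicting information. A form recording a patient alive on the visit date and a death form dated some days later can both be true, so case A may involve no conflict. Section 5.1 item 3 names the follow-up variable *deathyn* as the mortality measure. Visit windows are commonly set in the protocol, which is not at hand. These arguments stand against the timing examples. They do not reach C and D, which arise however promptly visits are made.

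It can also be said that a completed place of assessment usually means the patient was seen alive. That is fair, but section 2.1.1 itself provides for a completed place alongside a reported death, so it accepts that such records occur. Nor can the clash rule be stretched to cover C, because the sentence before it already assumes a patient with a blank death status to be alive. For D, section 6 items 2 and 3 do offer sensitivity analyses, but they treat a recorded death as unknown.

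A reader might go further and infer that mortality is fixed by the date of death at month 6, so that early or late visits by unblinded nurses would bias the treatment effect. The SAP does not support this. Section 2.1.2 states no cut-off day, and its date check is triggered by a reported death. A late visit would give the reverse pattern (0 in the primary outcome, possibly not a 6-month death). With constant hazards through the planning rates of 50% and 40% at 12 months, a two-week difference between arms in mean visit timing would move the risk difference by about 1.5 to 1.9 points. But nothing in the SAP suggests such a difference, and the figure counts residential care as well as death.

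**Conclusion.** The primary-outcome rule is wrong as written. It sets aside a filed death form when the visit entry for death is blank, so a documented death can be analysed as a success or as missing while section 2.1.2 counts it as a death. This rests on the text of the two sections, and on reading section 2.1.2 as accepting a filed death form when the follow-up entry is blank.

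The effect is probably small. It is a fraction of a point per patient on the planned denominators, and the number of such patients cannot be derived from the SAP. The early-visit case adds perhaps 2 to 8 patients on assumed mortality and visit timing, and only if the overrule sentence is read broadly. Bias between arms from visit timing is a possibility, not a finding. The change is still worth making, because the error sits in the primary outcome and costs almost nothing to remove.

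**What to change.** Define one 6-month death variable and use it in both outcomes:

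- Derive it from the Patient Death CRF and *deathdat*, against one stated cut-off after randomisation (day 183, for example), with the death form overruling the follow-up CRF.
- Set 'living at home' to 0 for every death on or before the cut-off, whatever the visit form says and whether or not its fields are blank.
- Keep the site query where neither form exists, and apply it to the primary outcome as well.
- State the coding once, since section 2.1.1 and section 5.1 item 3 code dead and alive in opposite directions.
- Apply the same construction at 12 months.

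For a death after the cut-off but before a late visit, residence should not be filled in by carrying forward the last recorded place. Appendix II schedules the preceding collection at 1 month, so the value would be about five months old. Because patients in residential settings are excluded at entry, it would also lean towards 'living at home'.

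The cost is a sentence or two in section 2.1.1, a cross-reference from section 2.1.2 and a few lines of derivation code, ideally settled before the 6-month analysis. No new data are needed, and the sample size is unchanged.

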2.1.2 SECONDARY OUTCOMES FOR THE PRIMARY OBJECTIVE

The secondary outcomes for the primary objective are: presence of delirium, mortality, new long-term residential care, cognitive impairment, activities of daily living, quality of life, quality adjusted survival, length of stay in hospital, readmission or transfer to hospital, resource use (health and social care and informal care), and costs and cost-effectiveness, see Appendix III for questionnaire scoring.

1) Incident and Persistent of Delirium (CAM) at baseline, 3 days, 5 days, and 1 month

The Confusion Assessment Method (CAM) diagnostic algorithm [1] is used to derive a variable for delirium, and is assessed at baseline, 3 days, 5 days and 1 month follow-up. CAM is split into 4 features (acute onset and fluctuating course, inattention, disorganized thinking, and altered level of consciousness).

Feature 1 (acute onset and fluctuating course) is present if there is evidence of an acute change in mental status from the patient's baseline (variable *cam1*) **AND** the behaviour fluctuated during the interview (variable *cam2b*). Feature 2 (inattention) is present if the patient had difficulty focusing attention during the interview in either mild or marked form (variable *cam2a*). Feature 3 (disorganized thinking) is present if the patient's thinking is disorganised or incoherent (variable *cam3*). Feature 4 (altered level of consciousness) is present if the patient's level of consciousness is anything other than alert (or uncertain) (variable *cam4*).

A diagnosis of delirium will be coded as a binary variable (0 = absent, 1 = present) and is present if the patient is positive for a presence of acute onset and fluctuating discourse (feature 1) **AND** positive for inattention (feature 2) **AND EITHER** disorganised thinking (feature 3) **OR** altered level of consciousness (feature 4).

If 'not applicable' is answered it shall be treated as 'no', and delirium will be calculated for each patient unless all the items from these sections are missing, in this case the delirium score will be coded as missing.

2) Mortality at 3 days, 5 days, 1 month, 6 months and 12 months

Patient mortality status is collected at 3 days, 5 days, 1 month, 6 months and 12 months after randomisation on the respective follow-up CRFs, date and details of a patient's death is collected on

the patient death form CRF. If a patient has been reported as dead at 6 or 12 months on the follow-up CRF (variable *deathyn*) it will be checked against the date of death on the Patient Death CRF (variable *deathdat*). If there is conflicting information between the follow-up form and the death form, the death form will overrule the Follow up CRF. If neither the follow-up form nor the death form have been completed then the TM will check with the site if the patient has died.

3) New long-term residential care at 1 month and 6 months

Subsequent admission to residential care is measured at 1 month, and 6 months follow up (variable *admitryn*). This will be coded as a binary variable (0 = No, 1 = Yes). The 6 months admission to residential care data will include the data collected at the 1 month time point.

4) Cognitive impairment at baseline and 6 months (MoCA)

The Montreal Cognitive Assessment (MoCA) [2] is used to derive a variable for cognitive impairment, and is assessed at baseline and 6 months follow-up. The MoCA comprises 8 sections with a total of 30 questions administered by a qualified health professional (variables *mocavis mocanam mocaatt mocalan mocaabs mocarec mocaori*). A total MoCA score will be derived by summing the score from each section of the questionnaire, only patients with complete MoCA will have a total MoCA score computed, an extra point is added to the total score if the patient has 12 or less years of education. The possible range of scores for the MoCA range from 0 to 30, with a score of 26 or above is considered normal. If the patient is visually impaired or if they are frail and unable to write and draw, the visuospatial/executive section (variable *mocavis*) and the naming section (variable *mocanam*) are excluded and is scored out of 22 instead, a score of 18 or above is considered normal. Cognitive impairment will be coded as a binary variable (0 = score less than 26 (less than 18 if visually impaired), 1 = score 26 or more (18 or more if visually impaired)).

5) Activities of daily living at baseline and 6 months (Barthel index)

The Barthel index [3] is used to derive a variable for activities of daily living, and is assessed at baseline and 6 months follow-up. The Barthel index consists of 10 questions (variables *biadl1 – biadl10*), and has a possible range of scores from 0 (completely dependent) to 20 (completely independent). The final Barthel index score is derived by summing the 10 items.

6) Known cognitive decline at baseline (IQCODE)

The Short Form of the Informant Questionnaire on Cognitive Decline in the Elderly (IQCODE) [4] is assessed at the patients baseline visit only. IQCODE is a 16 item questionnaire (variables *iqcode1 – iqcode16*), each question has a possible range of scores from 1 to 5. To obtain the mean IQCODE score for each participant take the mean of all IQCODE items available for that participant. Participants will still have their mean IQCODE score calculated if they are missing several items, participants will only be missing their mean IQCODE score if they are missing every item. Randomisation was stratified by IQCODE score ≥ 3.5

7) Quality of life at baseline and 6 months

Quality of life is measured by EQ-5D-5L scores [5], and is assessed at baseline and 6 months follow-up. EQ-5D-5L index scores will be computed as per the EQ-5D-5L user guide (version 2.1 April 2015).

8) Quality adjusted survival at 6 months and 12 months

Quality adjusted survival will be analysed as part of the economic evaluation and the methods will be detailed in a separate analysis plan.

9) Length of hospital stay over 6 months from randomisation

Number of nights spent in hospital between baseline and 6 months follow-up is collected on the health service use CRF.

10) Readmission or transfer to hospital at 1 month and 6 months

Subsequent admissions to hospital is measured at 1 month, and 6 months follow-up (variable *hadmityn*). Subsequent admissions to hospital is a binary variable (0 = No, 1 = Yes). The 6 months admission to hospital data will include the data collected at the 1 month time point. Number of days spent in hospital at 1 month, and 6 months after baseline will not be considered in the main statistical analysis, this data will be analysed as part of the economic evaluation and the methods will be detailed in a separate analysis plan.

11) Resource use (health and social care and informal care) at baseline and 6 months

Resource use will be analysed as part of the economic evaluation and the methods will be detailed in a separate analysis plan.

12) Costs and cost-effectiveness

Costs and cost-effectiveness will be analysed as part of the economic evaluation and the methods will be detailed in a separate analysis plan.

13) 'Living at home' at 12 months

Data on living in residential care and death will be collected from a range of sources, this will include the primary care and hospital record. Patient's GPs may be followed up over 12 months to collect information on admission to hospital and death. If this happens this outcome will be derived as per the primary outcome using place of assessment and patient's death status reported at the 12 months visit.

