Appendix III. Questionnaire scoring

Questionnaire	Possible range of scores	Higher or lower score indicates better health
Charlson Index (Comorbidity)	0-36	Lower
Barthel Index (Activities of daily living)	0-20	Higher
MOCA (Cognitive impairment)	0-30	Higher ≥26 is considered normal (≥18 is considered normal if visually impaired)
IQCODE short (background cognitive status)	1-5 (mean score across all questions)	Lower (3 indicates not much change in last 10 years)
EQ5D VAS (Health status)	0-100	Higher

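### SAP 2.1.2 item 4 contradicts itself on the MoCA cut-off for patients too frail to write: its definition sentence uses 18, but its coding line and Appendix III reserve 18 for the visually impaired

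*SAP*

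**What the plan says.** Three places in the SAP set the cut-off.

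- **Section 2.1.2 item 4, definition sentences.** For the full form: "The possible range of scores for the MoCA range from 0 to 30, with a score of 26 or above is considered normal". For the short form, two reasons are given: "If the patient is visually impaired or if they are frail and unable to write and draw, the visuospatial/executive section" and the naming section "are excluded and is scored out of 22 instead, a score of 18 or above is considered normal". The sentence does not limit the 18 to either reason.
- **Section 2.1.2 item 4, coding line.** This follows directly and defines the binary variable. Category 0 is "0 = score less than 26 (less than 18 if visually impaired") and category 1 is "1 = score 26 or more (18 or more if visually impaired"). Patients too frail to write appear in neither bracket.
- **Appendix III, MoCA row.** 26 or more is normal, and "≥18 is considered normal if visually impaired". Again only visual impairment is named.

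On the total score, item 4 adds that "an extra point is added to the total score if the patient has 12 or less years of education". Section 5.1 item 5 refers back to 2.1.2 for the binary variable and models it at 6 months, with an adjusted relative risk, confidence interval and p-value. Section 7 uses MoCA status as the subgroup factor in its single, exploratory, subgroup analysis.

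**The concern.** The coding line is what a programmer would implement, and Appendix III is where the SAP sends readers for scoring. Both leave out a group that the preceding sentence has just created. Followed to the letter, they compare a score on a 22-point scale with a threshold set for a 30-point scale.

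The group is foreseeable. Section 2 describes the trial population as older people with frailty and some disability, so physical inability to write is a plausible reason for using the short form. Under the literal coding line these patients would be recorded as cognitively impaired because of hand function or weakness, whatever their cognition. If the proportion differed between arms, the relative risk for cognitive impairment would partly reflect that difference.

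**Working it through.** **1. The SAP's own figures.** The full form is out of 30 and the short form out of 22, so 30 − 22 = 8 points are dropped. The full-form threshold less those points is 26 − 8 = 18, which is the stated short-form threshold. Both thresholds allow the same loss: 30 − 26 = 4 and 22 − 18 = 4. The 18 therefore belongs to the form, not to the reason for using it.

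**2. Scores open to a sighted patient too frail to write.**

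| | Range | Scores ≥ 26 (coding line read literally) | Scores ≥ 18 (definition sentence) |
|---|---|---|---|
| No education point | 0 to 22 | none of 23 | 5 (18 to 22) |
| With education point | 1 to 23 | none of 23 | 6 (18 to 23) |

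Under the literal coding line even a perfect short form is coded 0. Under the definition sentence, scores of 18 and above are coded 1. The two rules disagree for exactly those scores. (This treats a short form as a complete MoCA under the completeness rule, since scoring it out of 22 would otherwise serve no purpose.)

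**3. What the literal rule would do to the relative risk.** The SAP gives neither the short-form share nor the impairment rate, so every input here is an assumption chosen for illustration. Let s be the share of an arm on the short form for frailty, p the true impairment rate, and suppose p is the same whichever form is used.

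- Observed impaired = s + (1 − s)p
- Observed normal = (1 − s)(1 − p)

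*Equal share in both arms, true impairment 70% (inpatient) and 56% (hospital at home), true relative risk 0.80:*

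| s | Relative risk, event = impaired | Relative risk, event = normal |
|---|---|---|
| 5% | 0.582/0.715 = 0.81 | 0.44/0.30 = 1.47 |
| 10% | 0.604/0.730 = 0.83 | 1.47 |
| 20% | 0.648/0.760 = 0.85 | 1.47 |
| 30% | 0.692/0.790 = 0.88 | 1.47 |

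With normal as the event, the factor (1 − s) cancels and the ratio does not move.

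*Unequal share, no true effect (70% in both arms), s = 30% inpatient and 20% hospital at home:*

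- Event = impaired: (0.20 + 0.80 × 0.70)/(0.30 + 0.70 × 0.70) = 0.76/0.79 = 0.96
- Event = normal: (0.80 × 0.30)/(0.70 × 0.30) = 0.24/0.21 = 1.14

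Both should be 1.

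**4. Share misclassified in the equal-share scenario.** With 2:1 allocation the truly normal proportion is (0.30 + 2 × 0.44)/3 = 0.393, so the misclassified share of assessed patients is 0.393s: about 2.0%, 3.9%, 7.9% and 11.8% for the four values of s.

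**The case against.** The strongest reply is that the SAP already handles this case. The sentence just before the coding line gives 18 as normal for both groups. On that view, the coding line's mention of visual impairment is shorthand for the short form just described, and Appendix III repeats the shorthand in a single cell. Comparing a score out of 22 with 26 is so plainly wrong that a programmer would probably query it.

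Much of this stands. A reader who saw only the coding line and Appendix III might infer that the SAP has settled on 26 for patients too frail to write, so that they can never be coded normal. The documents do not support that as the plan's only rule, because the definition sentence says otherwise. What does not stand is the claim that nothing needs changing. The SAP nowhere says that visual impairment stands for the short form. The narrower wording appears three times (both coded categories and the appendix), and the coding line is the sentence that defines the analysed variable.

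A second reply concerns size. A reader might infer that the relative risk is necessarily pulled towards 1. That too goes further than the SAP allows. The written coding puts 1 on normal cognition; if that is the event modelled, an equal short-form share in both arms leaves the ratio unchanged and costs only precision. Attenuation at equal shares needs impairment to be the event. Nor does anything in the SAP indicate that the share differs between arms.

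**Conclusion.** The point holds as an internal contradiction: one sentence of section 2.1.2 item 4 applies the cut-off of 18 to both short-form groups, while the next sentence and Appendix III apply it to one. The consequence of the literal coding line is certain for the patients it reaches, since a maximum of 22 or 23 cannot meet 26.

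The effect on the trial result cannot be sized from the SAP. An unequal share between arms would bias the relative risk under either coding; an equal share attenuates it only when impairment is the event. The figures under the working show direction under assumed inputs and are not estimates for this trial.

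The reach is limited to cognitive impairment at 6 months as a secondary outcome and, through MoCA status, the exploratory subgroup analysis. It should be corrected because it is easy to prevent; it does not threaten the main conclusion.

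**What to change.** Make the cut-off depend on the form used, following the SAP's own definition sentence:

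- In the coding line of section 2.1.2 item 4, state that 18 or more is normal whenever *mocavis* and *mocanam* are excluded and the score is out of 22, for either of the two stated reasons, and that 26 or more is normal for the full form.
- Change the MoCA row of Appendix III to match.
- Write the derivation code to branch on whether those two sections were excluded, not on visual impairment.

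The cost is one sentence, one table cell and one line of code. No new threshold is introduced. No new data should be needed, because scoring out of 22 already requires knowing which patients had these sections excluded.
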